# 7.4 Study Populations

Subjects aged 35-60 that meet the eligibility criteria will be included in the study. No subgroup analysis is planned and subjects will not be stratified into different groups. Furthermore, there are no control groups as the achievement of a VA threshold is assessed for each eye and further analysis aims at assessing the improvement of VA from baseline to follow-up visit for each eye

# 7.5 Statistical Analysis

#### Primary analysis:

The analysis of the primary performance endpoint is based on Fleming's two-stage design. Threshold responder rates and observed responder rates will be compared to determine if the study is discontinued for futility or achievement of the performance endpoint. The performance endpoint is met and the null hypothesis will be rejected at least 48 responses were observed among the 54 eyes at the interim analysis or 73 responses of 86 eyes at the study end. Conversely, the study will be terminated prematurely for futility if 43 or less responses were observed among the 54 eyes at the interim analysis will be rejected if less than 73 responses were observed at the study end. This analysis yields a power of 80% and a one-sided type I error probability of 2.5% for the targeted sample size.

#### Secondary analysis:

The analysis of secondary performance endpoints will include summary statistics for continuous variables: Number of non-missing values, mean, SD, median, minimum, maximum and 95% exact binomial confidence limits.

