# 3.0 STUDY DESIGN

#### 3.1 Description of Study Design

This is a prospective, open-labeled, multi-site evaluation of clinical performance of the CE-Marked EDOF ICL for the improvement of UCNVA. Approximately 48 subjects who meet all eligibility criteria will undergo phakic IOL implantation in both eyes. All eyes will be followed for 6 months after surgery.

The first eye implanted with the study lens and the appropriate time for fellow eye implantation will be determined by the medical judgement of the Investigator. All eyes will be analyzed for safety and performance.

The subject will have completed the entire study when the study lenses have been implanted bilaterally and the Sponsor receives completed case report form (CRF) documentation for all visits. A Study Exit CRF for each eye must be completed for all subjects enrolled in the study.

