# 7.0 STATISTICAL METHODS

This section describes the statistical analyses intended at the time of investigation planning. Further details on the statistical and analytical aspects will be presented in the Statistical Analysis Plan (SAP).

Any deviations from planned analyses, the reasons for such deviations, and all alternative or additional statistical analyses that may be performed before database close will be described in amendments to the clinical protocol or the SAP. All deviations and/or alterations will be summarized in the clinical study report.

Continuous variables (values and changes from baseline) will be summarized by N, mean, SD, median, minimum, and maximum. For qualitative variables, absolute and percent frequencies (N, %) and, if applicable, shift tables will be displayed. Confidence limits will be given where appropriate.

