#### 7.2 Study Endpoints

#### 7.2.1 Performance Endpoints

The primary performance endpoint is defined as achievement of monocular UCNVA of Snellen equivalent 20/40 or better at 40 cm at Visit 5 (6 months after implantation) in equal to or greater than 75% of implanted eyes (responder rate).

Fleming's two-stage design was used, which enables early termination of the study at an interim analysis for futility or performance. Here, an interim analysis will be performed with the results obtained from 27 subjects (54 eyes). If there are 43 or less responses, the trial will be stopped for futility since the likelihood of still obtaining a significant result is too low to continue the study under ethical considerations. If there are 48 or more responses observed at the interim analysis, the trial will be stopped and the null hypothesis rejected as enough statistical evidence has been accrued to determine that, within the certainty of the controlled one-sided type I error probability of 2.5%, the true responder rate is greater or equal to 75%.

Otherwise, 16 additional patients (32 eyes) will be recruited for a total of 43 patients (86 eyes). The null hypothesis will be rejected if 73 or more responses are observed among the 86 eyes. This design yields a one-sided type I error probability of 2.5% and a power of 80% if the true response rate is 87.5%.

Secondary performance endpoints include the following:

- Percentage of implanted eyes achieving monocular UCNVA of Snellen equivalent 20/40 or better at 40 cm at Visit 3 and 4 (1 and 3 months after implantation respectively)
- Change from baseline in monocular uncorrected intermediate visual acuity (UCIVA) at 80 cm at postoperative Visit 3, 4 and 5
- Change from baseline in monocular UCNVA at 40 cm at postoperative Visit 3, 4 and 5
- Change from baseline in monocular distance corrected intermediate visual acuity (DCIVA) at 80 cm at postoperative Visit 3, 4 and 5
- Change from baseline in monocular distance corrected near visual acuity (DCNVA) at 40 cm at postoperative Visit 3, 4 and 5
- Change from baseline in binocular UCNVA at 40 cm at postoperative Visit 3, 4 and 5

There are no prespecified performance targets for secondary performance endpoints. 95% confidence limits will be calculated for all secondary performance endpoints.

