#### **Exploratory analysis:**

All additional variables will be summarized by summary statistics for continuous variables (including number of non-missing values, mean, SD, median, minimum, maximum) and frequency (N, %) for discrete variables.

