#### **Full Analysis Set:**

The FAS contains the data of each eye in the SES for which data has been collected for the primary performance endpoint.

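### Section 7.5 gives exact binomial limits for continuous variables, so five of the six secondary endpoints have no usable interval method, and pairing of eyes is ignored

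*Combined protocol and SAP*

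**What the plan says.** Section 7.2.1 lists six secondary performance endpoints. One is binary: the percentage of eyes reaching the near-acuity threshold at Visits 3 and 4. The other five are changes in visual acuity at Visits 3, 4 and 5: monocular UCIVA, UCNVA, DCIVA and DCNVA, and binocular UCNVA. A typical entry reads "Change from baseline in monocular UCNVA at 40 cm at postoperative Visit 3, 4 and 5". The section then commits to intervals throughout: "95% confidence limits will be calculated for all secondary performance endpoints".

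The method appears only in section 7.5, Secondary analysis, which plans "summary statistics for continuous variables: Number of non-missing values, mean, SD, median, minimum, maximum and 95% exact binomial confidence limits". The exploratory paragraph of the same section has nearly the same list without the binomial limits: "summarized by summary statistics for continuous variables (including number of non-missing values, mean, SD, median, minimum, maximum". Section 7.0 adds only that "Confidence limits will be given where appropriate" and leaves further detail to an SAP whose text is not among the supplied documents.

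On the unit of analysis, section 3.1 has both eyes implanted and states that "All eyes will be analyzed for safety and performance". Section 7.4 says that "further analysis aims at assessing the improvement of VA from baseline to follow-up visit for each eye". The analysis set is also defined by eye: "The FAS contains the data of each eye in the SES for which data has been collected for the primary performance endpoint".

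**The concern.** An exact binomial interval is built from a number of successes out of a number of trials. A change in visual acuity has no such count, so the stated method cannot be carried out for the five change endpoints. Their method would therefore be chosen later, in an open-label study.

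The second problem is pairing. Two eyes of one person share age, optics and measurement conditions, so their results are likely to be correlated. An interval that treats 86 eyes as 86 independent units is then too narrow. This affects the four monocular changes and the responder percentages. Binocular UCNVA is different: Appendix A yields one binocular value per subject per visit (baseline in Table A1, follow-up in Table A2), so the natural unit is the subject, but the plan does not say so.

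There is no control group, and section 7.4 makes improvement from baseline the aim of the further analysis. Readers will judge that improvement by these limits.

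**Working it through.** **1. Count of intervals, per analysis set.**
- Responder percentage: 1 endpoint × 2 visits = 2.
- Changes from baseline: 5 endpoints × 3 visits = 15.
- Total 17. The stated method fits 2 and leaves 15. Section 7.5 plans both FAS and PPS, which doubles both counts.

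**2. Inputs.** From section 7.3: 27 subjects (54 eyes) at the interim, 43 subjects (86 eyes) in total, a design rate of 87.5% and an expected rate of 90%. These rates refer to Visit 5; I use them as stand-ins for Visits 3 and 4. The documents give neither a fellow-eye correlation ρ nor an SD of change. I assume ρ = 0.3, 0.5 and 0.7, and give mean-change widths in SD units.

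**3. The plan's own figures.** None is given for the secondary intervals. As a check on the unit, the primary two-stage rule with eyes taken as independent gives P(X₁ ≥ 48 of 54) plus the sum over x = 44 to 47 of P(X₁ = x)·P(X₂ ≥ 73 − x of 32). At 75% this is 0.0096 + 0.0136 = 0.0232. At 87.5% it is 0.817. These agree with the stated 2.5% and 80%, so the plan does count eyes as independent.

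**4. Coverage of the exact interval for a responder percentage.** For each pair of eyes, P(both respond) = p² + ρp(1 − p) and P(exactly one) = 2p(1 − p)(1 − ρ). I convolved the pair totals over the subjects and summed the probability that the Clopper-Pearson 95% interval contains p.

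| Eyes | True rate | ρ = 0 | 0.3 | 0.5 | 0.7 |
|---|---|---|---|---|---|
| 86 | 87.5% | 96.8% | 94.0% | 92.0% | 89.9% |
| 86 | 90% | 95.4% | 92.0% | 89.5% | 87.2% |
| 54 | 87.5% | 98.0% | 95.8% | 94.2% | 92.5% |
| 54 | 90% | 96.0% | 92.7% | 90.3% | 88.2% |

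The 54-eye rows are not conditioned on the trial having stopped at the interim.

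**5. Mean change, if a per-eye t interval is used by default.** The plan does not prescribe this; it is the likely substitute. With two eyes per subject the variance of the mean is multiplied by 1 + ρ, so coverage is approximately 2Φ(1.96/√(1 + ρ)) − 1.
- ρ = 0.3: 1.96/1.140 gives 91.4%.
- ρ = 0.5: 1.96/1.225 gives 89.0%.
- ρ = 0.7: 1.96/1.304 gives 86.7%.

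Simulation with 100,000 normal trials gives 91.5%, 89.0% and 86.5% for 43 subjects, and 91.5%, 88.8% and 86.6% for 27.

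In widths, the per-eye half-width on 86 eyes is 1.988/√86 = 0.214 SD. Allowing for pairing (42 df) it is 2.018 × √((1 + ρ)/86), which is 0.248, 0.267 and 0.284 SD.

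**6. Check of the replacements.** A t interval on subject means covers 94.9 to 95.1% at 27 and 43 subjects for ρ from 0 to 0.7. Clopper-Pearson on an adjusted sample size, at 87.5%, covers 96.7 to 97.2% at 43 subjects and 95.7 to 98.0% at 27 (20,000 trials).

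**The case against.** The strongest reply is that this is a drafting slip. Set beside the exploratory paragraph, the sentence looks like two lists run together, and no analyst would compute binomial limits for a mean logMAR change. That is probably right about the cause. It does not close the gap: if the phrase was meant only for the percentages, the five change endpoints still have no method despite the promise in section 7.2.1.

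Second, section 7.0 defers detail to an SAP that was not available. An SAP could supply both the interval method and the handling of pairing, so the pairing point is a statement about the protocol text only. The misplaced phrase would still need correcting to agree with it.

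Third, the size depends on an assumed correlation. On 86 eyes at ρ = 0.1 and 0.2, exact coverage is 95.9% and 95.0% at a rate of 87.5%, and 94.3% and 93.2% at 90%. The prescribed method is therefore adequate at low correlation, and at 54 eyes with an 87.5% rate it stays close to nominal up to ρ = 0.5. The larger shortfall belongs to the per-eye t interval, which the plan does not name.

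Finally, no target or test is attached to the secondary endpoints. This stands and limits the weight of the point.

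**Conclusion.** The concern holds. As written, the only named interval method cannot be applied to five of the six secondary endpoints (15 of 17 intervals per analysis set). Where it can be applied, it treats fellow eyes as independent. Confidence is high on the wording, which needs no assumption. The pairing effect rests on the assumed ρ and on the supplied text containing no adjustment. At ρ between 0.3 and 0.7 and 86 eyes, the exact interval covers between 94.0% and 89.9% at a rate of 87.5%, and between 92.0% and 87.2% at 90%. A default per-eye t interval would cover about 91% to 87%. The consequence is overstated precision in descriptive results. No success or stopping decision changes, so this should be corrected but does not threaten the trial's main conclusion.

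**What to change.** In section 7.5, replace the phrase with one named method per endpoint type, and make the SAP agree.

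- **Four monocular changes:** a 95% interval for the mean change from a linear mixed model with a random subject intercept and Kenward-Roger degrees of freedom. It accepts subjects with one evaluable eye, which the eye-based FAS allows. With both eyes present it reduces to a t interval on subject means, unless the between-subject variance is estimated as zero; state in advance what is done then. GEE with subject as cluster or a subject-level bootstrap would also be acceptable.
- **Binocular UCNVA change:** a one-sample t interval with the subject named as the unit, and a rule for subjects with only one eye in the FAS.
- **Responder percentages at Visits 3 and 4:** Clopper-Pearson limits on the number of eyes divided by the design effect, with that effect estimated from the between-subject variance and held between 1 and 2. Show the unadjusted limits alongside. Coverage can fall a little below nominal at extreme values (just under 93% at a 95% rate with ρ = 0.7 and 43 subjects).

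The cost is one paragraph, minor programming and somewhat wider intervals. For 75 responders of 86, the unadjusted limits are 78.3 to 93.4%. With effective sizes 86/(1 + ρ) = 66.2, 57.3 and 50.6, they become 76.7 to 94.2%, 75.7 to 94.6% and 74.8 to 94.9%. No extra subjects or visits are needed.

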#### Safety analysis:

All AEs will be coded according to the Medical Dictionary for Regulatory Devices (MedDRA) version in effect at the time the database is closed. Incidences will be calculated for ocular and serious ocular and non-ocular AEs on the system organ class (SOC) level and on the preferred term (PT) level by intensity and by relationship to the study lens. Listings and, if applicable, tables displaying incidences of ocular AEs leading to discontinuation, serious AEs, and deaths will be provided.

#### **Exploratory analysis:**

All additional variables will be summarized by summary statistics for continuous variables (including number of non-missing values, mean, SD, median, minimum, maximum) and frequency (N, %) for discrete variables.

#### Analysis sets:

The analyses of the primary and secondary performance endpoints will be based on the Full Analysis Set (FAS) and Per Protocol Set (PPS). Safety analyses will be based on the Safety Evaluation Set (SES) and FAS. Further analyses will be based on the FAS and PPS.

#### Safety Evaluation Set:

The SES contains the data of each eye implanted with the study lens.

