	13. Subject who is pregnant, plans to become pregnant, or is lactating during the course of the study, or has another condition associated with the fluctuation of hormones that could lead to refractive changes,	
	14. Subjects who, in the judgment of the Investigator, present any emotional, physiologic, or anatomical condition which may preclude participation in this study or provide an inappropriate landscape for the intended study treatment.	
Investigational device:	The EDOF ICL includes a refractive optic and features a single piece lens design with a convex/concave optic zone of 4.9 to 6.1 mm diameter (according to model and power) and a 0.36 mm diameter central hole in the optic known as the KS-AquaPORT®. The lens is manufactured in five overall diameters: 11.6, 12.1, 12.6, 13.2, and 13.7 mm to accommodate different eye sizes. The lens is manufactured from Collamer, a proprietary polymer made from collagen, hydroxyethylmethacrylate (HEMA) and an ultraviolet (UV) absorber. The 10% UV cut-off for the ICL is at 387 nm wavelength. The lens is supplied with a delivery system for implantation through an incision of 3.5 mm or less.	
Study endpoints:	Performance Endpoints	
	Primary performance endpoint:	
	• Achievement of monocular UCNVA of Snellen equivalent 20/40 or better at 40 cm at Visit 5 (6 months after implantation) in equal to or greater than 75% of implanted eyes (responder rate)	
	Secondary performance endpoints include the following:	
	• Percentage of implanted eyes achieving monocular UCNVA of Snellen equivalent 20/40 or better at 40 cm at Visit 3 and 4 (1 and 3 months after implantation respectively)	
	• Change from baseline in monocular uncorrected intermediate visual acuity (UCIVA) at 80 cm at postoperative Visit 3, 4 and 5	
	• Change from baseline in monocular UCNVA at 40 cm at postoperative Visit 3, 4 and 5	
	• Change from baseline in monocular distance corrected intermediate visual acuity (DCIVA) at 80 cm at postoperative Visit 3, 4 and 5	
	• Change from baseline in monocular distance corrected near visual acuity (DCNVA) at 40 cm at postoperative Visit 3, 4 and 5	
	• Change from baseline in binocular UCNVA at 40 cm at postoperative Visit 3, 4 and 5	
	There are no prespecified performance targets for the secondary performance endpoints.	
	Safety Endpoint	
	• Ocular adverse event (AE) rates assessed in implanted eyes	
	There are no prespecified performance targets for the safety endpoint.	

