#### 3.2.3 Subject Discontinuation

A subject may be discontinued (at the discretion of the Investigator, the Sponsor and/or the EC) prior to the final study visit for several reasons, including, but not limited to:

- voluntary withdrawal
- death
- surgical complication preventing implantation of the study lens
- explant of the study lens(es)

If the study lens is explanted, a minimum of one post-explant visit should be completed to record safety measures for the subject (e.g., BCDVA, cataract/lens evaluation, endothelial cell count, etc.).

Prior to discontinuing a subject, every effort should be made to contact the subject, schedule a final study visit, and obtain as much follow-up data as possible.

Adverse events will be followed as described in Section 6.3.5. Subject withdrawals will be documented clearly on the source document and applicable CRF.

Only subjects who do not receive successful bilateral implantation MAY be replaced. Subjects who are discontinued from the study following treatment will not be replaced.

Discontinued subjects should be followed outside of the study protocol according to the Investigator's normal postoperative standard of care.

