# 5.0 STUDY CONDUCT

# 5.1 Study Visits

All Subjects who meet the eligibility criteria will be seen according to the following schedule.

Preoperative Visit	Days -90 to 0
Operative Visit	Day 0
Postoperative Visit 1	Day 1 (1 day)
Postoperative Visit 2	Week 1 (5 – 9 days)
Postoperative Visit 3	Month 1 (3 – 5 weeks)
Postoperative Visit 4	Month 3 (10 – 14 weeks)
Postoperative Visit 5	Month 6 (21 – 26 weeks)

Refer to Appendix A for a schedule of visits and parameters and Appendix C for methods of clinical evaluation.

Following identification of a potential subject, the Investigator (or designee) will explain the purpose of the study, procedures, risks/benefits, and subject responsibilities to the potential subject. The subject's willingness and ability to meet the follow-up requirements of the study will be determined. If the subject chooses to participate in the investigation, written informed consent will be obtained. The subject and the person obtaining written consent, will sign and date the EC-approved ICF. The original signed document will be retained in the subject records, and a copy will be provided to the subject. In addition, the applicable privacy regulation requirements must be met.

#### 5.1.1 Preoperative Visit – Days -90 to Day 0

Prospective subjects who have provided informed consent will be screened to determine eligibility for treatment in the study. Demographic information, relevant ocular medical history, and current ocular medication use will be collected. The preoperative clinical evaluation will consist of a complete ophthalmic examination conducted no more than 90 days prior to surgery.

Refer to Appendix A: Schedule of Visits and Parameters for assessments to be performed.

#### 5.1.2 Operative Visit – Day 0

Subjects will be reassessed to confirm eligibility. In addition, any changes in concomitant medications or AEs will be recorded. If the subject no longer meets eligibility criteria, he/she will be considered a screen failure. If the subject is eligible, he/she will be enrolled in the study and undergo surgery according to the surgical procedure described in Appendix C. If the study lens is not implanted due to a surgical complication, the subject will be discontinued from the study.

At approximately 1-6 hours after surgery, an intraocular pressure (IOP) reading in the implanted eye(s) will be conducted. Any complications, AEs, or associated treatment given will be appropriately documented and reported.

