#### 7.2.2 Safety Endpoint

Ocular AE rates will be assessed for all implanted eyes. There are no prespecified performance targets for the safety endpoint.

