#### Per Protocol Set:

The PPS contains data of each eye in the FAS without major protocol deviations. Protocol deviations are further classified in the SAP.

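### The safety endpoint and safety set count only implanted eyes, so a complication that prevents implantation falls outside the ocular AE rate and no attempted-eye rate is defined

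*Combined protocol and SAP*

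**What the plan says.** Three places fix the safety denominator, and all of them condition on implantation.

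- Synopsis, Safety Endpoint: "Ocular adverse event (AE) rates assessed in implanted eyes".
- Section 7.2.2: "Ocular AE rates will be assessed for all implanted eyes". No target is set.
- Section 7.5, Safety Evaluation Set: "The SES contains the data of each eye implanted with the study lens".

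Section 7.5, Analysis sets, adds: "Safety analyses will be based on the Safety Evaluation Set (SES) and FAS". The second of these sets is no wider than the first: "The FAS contains the data of each eye in the SES for which data has been collected for the primary performance endpoint".

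The plan expects that some operations may not end with a lens in the eye. Section 3.2.3 lists a surgical complication preventing implantation among the reasons for discontinuation. Section 5.1.2 enrols the subject at the operative visit and then states: "If the study lens is not implanted due to a surgical complication, the subject will be discontinued from the study". On replacement, Section 3.2.3 says: "Only subjects who do not receive successful bilateral implantation MAY be replaced".

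The event is collected. Section 6.0 starts AE collection at consent, and Section 6.1.1 requires complications during surgery on the study eye to be recorded as AEs, whether or not the lens was implanted. The safety analysis paragraph of Section 7.5 plans listings and, if applicable, incidence tables of ocular AEs leading to discontinuation and of serious AEs. It gives no denominator of attempted eyes.

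**The concern.** Eyes leave the safety set because of an adverse outcome. An eye whose operation is abandoned because of a complication is, almost by definition, an eye with an ocular AE, yet it drops out of both parts of the ocular AE rate. What remains is an AE rate given successful implantation, not the rate for the procedure a patient agrees to undergo. It is too low as a measure of procedural risk whenever an implantation fails. Replacing the subject would then fill the planned sample with an implanted case.

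This is the trial's only safety endpoint, so no other planned rate makes up for the gap. The stakes are limited: the endpoint is descriptive, has no target, and plays no part in the two-stage performance rule.

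**Working it through.** **The plan's own figure.** The only stated eye count that can stand for attempted eyes is planned enrolment (Section 7.3). It reproduces: 43/0.9 = 47.8, rounded up to 48 subjects, or 96 eyes. The safety endpoint has no assumed rate or precision to reproduce.

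**Assumed inputs.** The documents give neither a failed-implantation rate nor an AE rate. I take k = 1 to 3 subjects with one failed eye each, every failure being a reportable AE, and an AE rate p of 0 to 20% in implanted eyes.

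**Attempted eyes.** Let N be planned eyes. A subject with a failed implantation is discontinued (Section 5.1.2) and may be replaced (Section 3.2.3). In every case attempted = implanted + k.

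| Failed eye | Replaced | Attempted | Implanted |
|---|---|---|---|
| First (fellow eye not operated) | no | N − k | N − 2k |
| First | yes | N + k | N |
| Second | no | N | N − k |
| Second | yes | N + 2k | N + k |

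**Rate missing from the endpoint**, k / attempted, at N = 96:

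- k = 1: 1/98 = 1.02% to 1/95 = 1.05%
- k = 2: 2/100 = 2.00% to 2/94 = 2.13%
- k = 3: 3/102 = 2.94% to 3/93 = 3.23%

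The exact (Clopper-Pearson) 95% limits are 0.03 to 5.55% for 1/98, 0.03 to 5.73% for 1/95, 0.61 to 8.36% for 3/102 and 0.67 to 9.14% for 3/93.

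**Gap between the two AE rates.** With I implanted eyes, the attempted-eye rate is (pI + k)/(I + k). Subtracting p gives (k / attempted) × (1 − p). Over p = 0 to 20%:

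- k = 1: 0.8/98 = 0.82 points to 1/95 = 1.05 points
- k = 2: 1.6/100 = 1.60 points to 2/94 = 2.13 points
- k = 3: 2.4/102 = 2.35 points to 3/93 = 3.23 points

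For example, take 96 attempted eyes, three failures and five other eyes with an AE. The planned rate is 5/93 = 5.4%; per attempted eye it is 8/96 = 8.3%.

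**Stop at the interim.** With the 54 eyes that Section 7.3 says are enrolled before the interim, the missing rate is 1/56 = 1.79% to 1/53 = 1.89% for one failure, and 3/60 = 5.00% to 3/51 = 5.88% for three.

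**No failures.** The bias is zero, but the figure is still informative. An explicit 0/96 gives an upper exact 95% limit of 1 − 0.025^(1/96) = 3.77%, and 0/54 gives 6.60%.

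All intervals treat the two eyes of a subject as independent.

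**The case against.** The strongest reply is that the event is not hidden. It must be recorded as an AE (Section 6.1.1), and it is reported within 24 hours if serious or device-related (Section 6.3.1). A Study Exit CRF is required for each eye of every enrolled subject (Section 3.1), and listings of AEs leading to discontinuation are planned. With a handful of events, a listing plus a count of operated eyes would tell the reader much the same. This stands as far as data capture goes. It does not supply a rate, and because safety analyses are tied to the SES and FAS, it is unclear whether even the listings would admit a non-implanted eye.

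Section 3.1 also says that all eyes will be analysed for safety. It names no denominator and does not override the specific definitions in Sections 7.2.2 and 7.5; the wording should be reconciled. Section 7.0 defers detail to the SAP. Nothing in the text available here widens the set; an attempted-eye summary elsewhere cannot be excluded, but the protocol definitions would still need to agree with it.

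The magnitude is open to challenge, and fairly so. The counts are assumed. A supplemental lens is supplied for each eye (Sections 4.1 and 4.3), so a damaged lens need not mean a failed implantation. The replacement cases run to 97 to 102 attempted eyes, beyond the ceiling of 96 in Section 3.2. If the interim enrolment were inflated for 10% attrition to 30 subjects (60 eyes), the missing rates would be 1/62 = 1.6% to 1/59 = 1.7% for one failure and 3/66 = 4.5% to 3/57 = 5.3% for three. None of this changes the direction.

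Finally, an implanted-eye rate is a legitimate measure for six-month follow-up. I agree, and it should be kept.

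**Conclusion.** The concern holds. As written, the ocular AE rate is conditional on successful implantation, and an event that the plan foresees and collects is excluded from it. At full enrolment, one to three failed implantations would leave a rate of roughly 1 to 3% unreported and put the planned rate about 0.8 to 3.2 points below the attempted-eye rate. At an interim stop with 54 eyes, the unreported rate would be about 1.8 to 5.9%. These sizes rest entirely on assumed counts, on each failure being a reportable AE, and on an AE rate of 0 to 20% in implanted eyes. If no implantation fails, there is no bias. The performance decision is untouched, so this is a worthwhile correction, not a critical fault.

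A smaller related point: the FAS requires primary-endpoint data from Visit 5, so FAS safety tables can lose explanted eyes or eyes lost to follow-up. They are supplementary, since Section 7.2.2 already makes the SES the endpoint population.

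**What to change.** - Define the safety set as every eye in which study-lens surgery was started, including eyes of subjects later replaced, and align the Synopsis and Section 7.2.2 with it.
- On that denominator, report the rate of complications preventing implantation and the rate of intraoperative AEs, also when the count is zero.
- Keep the ocular AE rate in implanted eyes beside it as the six-month follow-up measure.
- State that the FAS and PPS remain restricted to implanted eyes. Both derive from the SES (for the PPS: "The PPS contains data of each eye in the FAS without major protocol deviations"), so this leaves the performance analyses unchanged.
- Label the FAS safety tables as supportive.

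The cost is a wording amendment with EC approval before implementation (Section 8.6). The intraoperative event is already recorded, so it needs no new data. The reported rate may be slightly higher. Discontinued subjects are followed outside the protocol (Section 3.2.3), so abandoned eyes have shorter follow-up. The attempted-eye rate is therefore not a six-month AE rate and must be presented separately. A lighter alternative is a supplementary table of eyes with surgery started, eyes not implanted and the reason. That would give the missing denominator but leave the endpoint definition as it is.
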